7.4 Adverse Event Monitoring

Adverse event data collection and reporting, which are required as part of every clinical trial, are done to ensure the safety of subjects enrolled in the studies as well as those who will enroll in future studies using similar agents. Adverse events are reported in a routine manner at scheduled times during a trial. Additionally, certain adverse events must be reported in an expedited manner to allow for optimal monitoring of subjects' safety and care.

All subjects experiencing an adverse event, regardless of its relationship to study drug, will be monitored until:

- the adverse event resolves or the symptoms or signs that constitute the adverse event return to baseline;
- any abnormal laboratory values have returned to baseline;
- there is a satisfactory explanation other than the study drug for the changes observed; or
- death.

7.3.1 Definitions

An adverse event is defined as any untoward or unfavorable medical occurrence in a human research study participant, including any abnormal sign (for example, abnormal physical exam, imaging finding or clinically significant laboratory finding), symptom, clinical event, or disease, temporarily associated with the subject's participation in the research, whether or not it is considered related to the subject's participation in the research.

Adverse events encompass clinical, physical and psychological harms. Adverse events occur most commonly in the context of biomedical research, although on occasion, they can occur in the context of social and behavioral research. Adverse events may be expected or unexpected.

Acute Adverse Events

An adverse event is defined as any untoward or unfavorable medical occurrence in a human research study participant, including any abnormal sign (for example, abnormal physical exam or laboratory finding), symptom, clinical event, or disease, temporarily associated with the subject's participation in the research, whether or not it is considered related to the subject's participation in the research. Adverse events occurring through the time period of **the start of treatment through the first follow up occurring 12 weeks post treatment** will be considered acute adverse events. All acute adverse events will be assessed and reported as per below.

Late Adverse Events

Adverse effects occurring in the time period from the **end of acute monitoring**, to 3 years post treatment for progression or death (whichever comes first), will be defined as late adverse events. These events will include all adverse events reported directly to a member of the study team and will be captured, assessed, graded and reported as appropriate.

In addition, the study team will review encounters in a select specialty category relevant to study endpoints. These select specialties include hospitalizations, medical oncology, and radiation oncology records and will be limited in scope based on categorization of events (**GU/GI**) and also the type of records that will be queried (hospitalizations, **medical oncology, and radiation oncology**).

Adverse events encompass clinical, physical and psychological harms. Adverse events occur most commonly in the context of biomedical research, although on occasion, they can occur in the context of social and behavioral research. Adverse events may be expected or unexpected.

Severity

Adverse events will be graded by a numerical score according to the defined NCI Common Terminology Criteria for Adverse Events (NCI CTCAE) and version number

specified in the protocol. Adverse events not specifically defined in the NCI CTCAE will be scored on the Adverse Event log according to the general guidelines provided by the NCI CTCAE and as outlined below.

- Grade 1: Mild
- Grade 2: Moderate
- Grade 3: Severe or medically significant but not immediately life threatening
- Grade 4: Life threatening consequences
- Grade 5: Death related to the adverse event

Serious Adverse Events

ICH Guideline E2A and the UTSW IRB define serious adverse events as those events, occurring at any dose, which meets any of the following criteria:

- Results in death
- Immediately life-threatening
- Results in inpatient hospitalization or prolongation of existing hospitalization
- Results in persistent or significant disability/incapacity
- Results in a congenital anomaly/birth defect
- Based upon appropriate medical judgment, may jeopardize the subject's health and may require medical or surgical intervention to prevent one of the other outcomes listed in this definition.

Note: A "Serious adverse event" is by definition an event that meets **any** of the above criteria. Serious adverse events may or may not be related to the research project. A serious adverse event determination does not require the event to be related to the research. That is, both events completely unrelated to the condition under study and events that are expected in the context of the condition under study may be serious adverse events, independent of relatedness to the study itself. As examples, a car accident requiring >24 hour inpatient admission to the hospital would be a serious adverse event for any research participant; likewise, in a study investigating end-stage cancer care, any hospitalization or death which occurs during the protocol-specified period of monitoring for adverse and serious adverse events would be a serious adverse event, even if the event observed is a primary clinical endpoint of the study.

¹Pre-planned hospitalizations or elective surgeries are not considered SAEs. Note: If events occur during a pre-planned hospitalization or surgery, that prolong the existing hospitalization, those events should be evaluated and/or reported as SAEs.

² NCI defines hospitalization for expedited AE reporting purposes as an inpatient hospital stay equal to or greater than 24 hours. Hospitalization is used as an indicator of the seriousness of the adverse event and should only be used for situations where the AE truly fits this definition and NOT for hospitalizations associated with less serious events. For example: a hospital visit where a patient is admitted for observation or minor treatment (e.g. hydration) and released in less than 24 hours. Furthermore, hospitalization for pharmacokinetic sampling is not an AE and therefore is not to be reported either as a routine AE or in an expedited report.

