Therefore, we propose a single institution, safety lead-in phase II trial with SABR to multiple metastatic sites concurrently administered with Nivolumab for patients with metastatic clear cell renal cell cancer who have failed at least one anti-angiogenic therapy. This phase two trial tests the hypothesis that addition of SABR to Nivolumab is a durably effective means of potentiating the effects of PD-1 blockade in inducing higher objective response rate (RR) eventually leading to improvements in progression-free survival, complete response rate, overall survival without degrading quality of life in the mRCC patient population. As reported in prior trials, the RR for Nivolumab (dosing as per the institution guidelines, q 3 weeks until progression) in mRCC is 22%-25% [5, 56]. In the same trials, median OS was 25 months, and PFS was 4-4.6 months. The primary endpoint of this study is to measure improvement in response rate (RR) when SABR is added to Nivolumab compared to the RR in the reported historical control arm with Nivolumab alone. We will propose that the addition of SABR to Nivolumab will increase the RR to 43.8% i.e. 75% increase compared to the historical RR with Nivolumab alone. In our current ongoing phase II clinical trial (STU 012013-041) with similar patient population and treatment strategy of SABR + immunotherapy using IL-2, we are noticing a 53% RR with the combination whereas the historically reported response rate of IL-2 alone treatment is 20% (1). Therefore, we have increased the RR by >150%. Therefore, in oncology clinical trials, it is not uncommon to see such increases since the baseline RR is often low. The secondary objectives of this trial will measure progression-free survival (PFS), overall survival (OS), time to progression (TTP), complete response rate (CRR), duration of treatment response, and health related quality of life outcomes (HR-QoL). In addition, the exploratory objectives will include correlation of the immune response to clinical outcome, evaluation of immunologic biomarkers to predict response and explore possible mechanism of immune resistance. This will help us identify patients who may be more responsive to this regimen. Given the high cost of Nivolumab, it would be also interesting to evaluate the cost-effectiveness of adding SABR upfront with the hope that it would have cost saving effects and improve the quality-adjusted life-years for patients.

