Treatment with immunotherapies has been reported to cause a “tumor flare” which denotes the apparent radiographic increase in tumor burden or occurrence of new lesions before a true clinical response can be established. This “flare” is thought to be due to a transient increase in immune cell infiltration while the immune system is being primed. Therefore, RECIST criteria may fail to accurately report RR and some patients will be taken off therapy before a true response is measured. In the CheckMate 025 trial, 44% of patients who progressed per RECIST criteria were continued on Nivolumab if they were thought to have clinical benefit. In addition, in the phase II trial of Nivolumab dose escalation trial, treatment beyond first RECIST-criteria progression was allowed in patients who tolerated Nivolumab and exhibited investigator-assessed clinical benefit. 17%, 22% and 26% of patients in the 0.3, 2 and 10 mg/kg groups were treated beyond progression. Median number of doses received after RECIST progression was 4.5, 7.5 and 8.5 in the 0.3, 2 and 10 mg/kg groups. Median PFS was 2.7 mos, 4.0 mos and 4.2 mos in the 0.3, 2 and 10 mg/kg groups using the RECIST criteria but increased to 4.3, 5.4 and 6.9 mos respectively using immune-response PFS. In a subgroup analysis, 69% (25/36) of patients who received treatment beyond first progression, defined as patients receiving their last Nivolumab dose >6 weeks after RECIST-defined progression, demonstrated sustained reductions in tumor burden or lesion stabilization with an acceptable safety profile. Median OS for patients treated beyond first progression was 22 mos vs 12 mos for those not treated. Thus, patients will be allowed to stay on Nivolumab after their first RECIST-criteria progression per the treating physician. Data will be evaluated using the RECIST criteria for primary endpoint and ir-RECIST for secondary endpoint.

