The SABR prescription dose will be delivered to the periphery of the planning target volume (PTV, see below for definitions). Investigators will have discretion in choosing from either of the biologically equivalent dose levels using one or three fractions, although a single fraction is preferred over three fraction treatments. Treating physician will have further discretion in selecting the number and location of sites to treat if multiple sites of disease are present. Maximum number of lesions treated is deemed as feasible per the treating radiation oncologist. Physicians will be **REQUIRED** to leave at least one site of disease for the purpose of measuring a radiographic response (see section 6) at a non-treated site, as this is part of the primary endpoint. If left untreated, this site can be treated once patient meets the definition of progressive disease (PD) (see section 6). To clarify the definition of “site”, each site is an area or organ with active extracranial disease (≤ 3 in the liver = one site and ≤ 3 in the lung = one site) identified by CT scan, or PET/CT, within 4 weeks prior to initiation of SABR (up to 2 contiguous vertebral metastasis will be considered a single site of disease). For example: a patient with 4 right axillary lymph nodes, L1-L2 bone metastasis, 3 right lung lesions, 1 left lung lesion, 2 liver lesions, and

T2-T3 bone metastasis would be defined as having 6 sites of disease. Preference should be given to the largest feasible disease site, symptomatic sites and sites where palliative and preventative (i.e. to prevent a pathologic fracture in weight bearing bone, impending cord compression, impending SVC compression etc.) indications are applicable. The gross target/tumor volume (GTV) should be at least 2 cm³ in size, corresponding to roughly a 1.5 cm diameter tumor. This is to ensure that adequate tumor volume and therefore adequate tumor cells (roughly 10⁸ -10⁹ cells/cm³ [94]) are killed for antigen presentation. Treating physicians should choose their dose based on established planning guidelines at their center including their ability to respect normal tissue tolerance listed below. It is not required that all targets be treated with the same dose fractionation. A dose from the following table should be used:

Table 4.1.1 Prescription Dose

Number of Fractions	Total Cumulative Dose Encompassing 95% of Planning Target Volume (Gy)		
	Protocol Compliant	Minor Deviation *	Major Deviation
1	24-27 Gy	≥16 Gy, <24 Gy	<16 Gy

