4.4 Duration of Follow Up

For patients who respond to treatment, subjects will be followed for five years or until death (although findings will be analyzed and reported at a median follow up of 2-4 years), whichever occurs first. For these patients, follow-up will be every 8 - 12 weeks from study registration with imaging studies and physical exam (recommended) every 8-12 weeks for the first year, then every 8-12 weeks for the second year, then every four-six months thereafter for a total of five years.

Subjects who show progressive disease will be followed for survival and will no longer strictly adhere to study calendar requirements.

Subjects removed from treatment for unacceptable adverse events will be followed until resolution or stabilization of the adverse event.

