5.3 Follow-up Procedures

- For patients who are still receiving Nivolumab:

Subject will be followed every 8-12 weeks starting from the date of registration for the first two years. , then every four-six months thereafter for five years or death, whichever comes first. The following procedures will be performed at each follow up:

- Physical exam (recommended), Performance Status (recommended), Vital Signs, Medication Review, AE assessment
- HR-QoL questionnaire at baseline, and then at six month intervals until patient meets primary endpoint
- Blood collection for correlative immunologic studies (see section 9.0): In total, all patients will get blood draws for correlative studies at baseline, follow up q 8-12 weeks (until discontinued or within first year of enrollment, whichever is first) and at 1 year (if discontinued before 1 year).
- Radiographic imaging: Tumor assessments will be completed by the investigator using the RECIST and ir-RECIST criteria as above.
 - CT chest, abdomen and pelvis with IV contrast (contrast recommended), if allowable by renal function. MRI with contrast (contrast recommended) can replace CT.
 - MRI, if necessary to confirm CT findings, at the discretion of physician

- For patients who have been discontinued from Nivolumab (See Section 4.3): Subject will be followed within 3 months from last dose ((+/- 2 months), or may be on date of discontinuation).

The following procedures will be performed:

- Physical exam (recommended), Performance Status (recommended), Vital Signs, Medication Review, AE sssessment
- Subsequent anti-cancer treatment/s
- Blood samples for correlation immunologic studies

After that, survival visits/phone calls continue annually to include Survival Status, AE Assessment, and Subsequent anti-cancer treatment/s.

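### The late adverse-event window in Section 7.3.1 appears to close at progression: the median patient gets about 0-8 of a nominal 144 weeks, and later events have no defined place in the late count

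*Combined protocol and SAP*

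**What the plan says.** Section 7.3.1 splits adverse events into two periods. Acute events run from "the start of treatment through the first follow up occurring 12 weeks post treatment". Late events run from the end of that period "to 3 years post treatment for progression or death (whichever comes first), will be defined as late adverse events". Neither sentence says whether the treatment in question is SABR or nivolumab.

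Other sections bear on what happens around progression:

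- Section 1.4.2 gives the historical nivolumab results: "median OS was 25 months, and PFS was 4-4.6 months".
- Section 2.1 says that "patients will be allowed to stay on Nivolumab after their first RECIST-criteria progression per the treating physician". Sections 4.2.1.1 and 5.5.4 also allow this.
- Section 4.1.1 allows the disease site left unirradiated for response assessment to be treated once progressive disease is met.
- Section 4.4: "Subjects who show progressive disease will be followed for survival and will no longer strictly adhere to study calendar requirements".
- Section 5.3 schedules AE assessment at each follow-up while nivolumab continues and at a visit around 3 months after the last dose. Then: "After that, survival visits/phone calls continue annually to include Survival Status, AE Assessment, and Subsequent anti-cancer treatment/s". None of these contacts is said to stop at progression.

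**The concern.** Progression is usually the first of the three possible end points in this population. If it closes the late window, most of the nominal 3 years is never observed, and observation stops at an event related to outcome rather than at a fixed time. Exposure can meanwhile continue (nivolumab beyond progression) or be added (irradiation of the remaining site) after late counting has ended.

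Tolerability and toxicity are a secondary objective (2.2.7), and Section 1.4.2 concedes that side-effect data on the combination are sparse. The dose-constraint text and tables in Section 4.1.3.2 name airway occlusion from fibrosis, stenosis or fistula, myelitis and fracture as harms to guard against. A late-toxicity summary built on the 7.3.1 definition would rest on little person-time, and a low figure could partly reflect the window.

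**Working it through.** The plan states no figure for the length of the late window or for the number of patients at risk in it, so there is none to reproduce.

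**Inputs**
- Median PFS 4-4.6 months and median OS 25 months (Section 1.4.2).
- Immune-response PFS of 5.4 and 6.9 months in the two higher dose groups (Section 2.1). This is relevant because Section 2.4.3 defines progression by ir-RECIST. The lowest dose group's 4.3 months lies inside the 4-4.6 range.
- SABR timing: one week after the first dose (Section 2.0), two weeks after the second (4.1), or between the second and fourth (4.3).
- Assumed: dosing every 3 weeks (the interval in Section 1.4.2), registration at about the first dose, exponential PFS and OS, 52.18/12 = 4.348 weeks per month.

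**Median PFS in weeks.** 4 × 4.348 = 17.4; 4.6 × 4.348 = 20.0; 5.4 × 4.348 = 23.5; 6.9 × 4.348 = 30.0.

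**Nominal window.** 3 years less the 12 acute weeks: 156 − 12 = 144 weeks.

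**Median patient's window** = median PFS − end of acute monitoring (a). **Share progression-free at opening** = exp(−ln 2 × a / median).

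| a (weeks) | Basis | Window, PFS 4.0 | PFS 4.6 | PFS 5.4 | PFS 6.9 | Progression-free at opening (PFS 4.0 / 4.6) |
|---|---|---|---|---|---|---|
| 12 | 12 weeks from start | 5.4 | 8.0 | 11.5 | 18.0 | 62% / 66% |
| 13 | SABR week 1 | 4.4 | 7.0 | 10.5 | 17.0 | 60% / 64% |
| 17 | SABR week 5 | 0.4 | 3.0 | 6.5 | 13.0 | 51% / 55% |
| 21 | SABR week 9 | −3.6 | −1.0 | 2.5 | 9.0 | 43% / 48% |

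A negative entry means that the median patient progresses before the window opens, so it counts as zero. Of 21 patients, 0.43 × 21 ≈ 9 to 0.66 × 21 ≈ 14 would enter the window.

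**Mean late time observed** = [exp(−λa) − exp(−λ(a + 144))] / λ, with λ = ln 2 / median.
- Stopping at progression, PFS 4.0 months, a = 21: 10.8 weeks, or 10.8/144 = 7.5%.
- Stopping at progression, PFS 4.6 months, a = 12: 18.9 weeks, or 18.9/144 = 13.1%.
- Stopping only at death or 3 years, OS 25 months (108.7 weeks): 60.6% at a = 12 and 57.2% at a = 21.

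**If the anchor is the last nivolumab dose.** Acute monitoring then runs 12 weeks past that dose. For anyone who stops nivolumab at progression, the late window closes before it opens.

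**What still captures later events.** Section 5.3 schedules AE assessment as above. Section 7.4 follows an event already under way until it resolves, is otherwise explained, or the patient dies. Section 7.6 requires reporting of events more than 30 days after the last dose if attributed to the agents, with no end date. Section 7.7.1 requires SAEs to be notified during the study or within 30 days of the last dose. None of these says whether an event after progression belongs to the late category of 7.3.1.

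**The case against.** The strongest reply is that the sentence does not plainly say what is attributed to it. Read literally, it could mean 3 years after treatment, or after treatment for progression. That stands as a caution. But a first-to-occur clause needs competing end points, and 3 years, progression and death are the only ones named. A reader who rejects that reading is left with a window that has no determinable end.

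A reader might infer that late harm simply goes uncounted, or that AE collection stops at progression. The documents do not support that: Sections 5.3, 7.4, 7.6 and 7.7.1 keep many later events in view. Each has limits. Section 7.4 deals with events already present, 7.6 refers to the agents and sits among the expedited-reporting steps, and the later contacts in 5.3 are annual.

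A reader might also infer that the trial will report a falsely low late-toxicity rate. Section 11.3 plans only an overall toxicity rate with an exact interval, without an acute/late split. Section 6.2 analyses everyone with at least one SABR fraction and one nivolumab cycle, with no cut at progression. The primary endpoint and the six-patient safety review at 8 weeks are untouched. So the risk is to any summary that uses the 7.3.1 categories, not to a pre-specified late-toxicity test.

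Sections 4.4 and 5.3 can be read together, since 4.4 only relaxes the calendar. But 4.4 names survival alone as what is followed, so it leaves open whether the AE assessments remain required.

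Finally, the window is not empty for everyone, and it lengthens if SABR prolongs PFS as the trial hopes. Both are true and are reflected in the ranges given.

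**Conclusion.** The concern holds in a limited form. On its most natural reading, the 7.3.1 rule cuts the late window at an outcome-related event. It leaves the median patient about 0-8 weeks of a nominal 144 at the historical PFS, or about 2.5-18 weeks at the immune-response PFS of 5.4-6.9 months. Between 43% and 66% of patients would still be progression-free when it opens at the historical PFS. About 7-13% of nominal late time would be observed, against 57-61% if only death or 3 years ended it.

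The rule conflicts with the AE assessments in 5.3 and with treatment permitted after progression, and events found later have no defined place in the late count. These figures rest on exponential PFS and OS, historical PFS and OS applied to the combination, registration at about the first dose, every-3-week dosing, and SABR timings on which the protocol disagrees with itself.

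**What to change.** - **Section 7.3.1:** state one explicit anchor for *post treatment*, used for both the acute and the late period. End the late window at 3 years from that anchor, death, withdrawal of consent or end of study follow-up, whichever is first. State that progression does not end AE collection.
- **Section 4.4:** state that patients who have progressed keep the AE assessments already scheduled in Section 5.3.
- **Reporting:** list late events by onset before or after progression or next therapy.
- **SABR timing:** the sponsor must reconcile Sections 2.0, 4.1 and 4.3, because the end of the acute period depends on it if SABR is the anchor.

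The cost is mainly protocol wording, since 5.3 already schedules these contacts and records subsequent treatment. Ending at study follow-up keeps the window within the 3 years of follow-up in the Study Summary, whichever anchor is chosen. The small downside is that events after next-line therapy are harder to attribute, which the split listing handles.

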4.1.3 SABR Treatment Technique

4.1.3.1 Simulation, beam arrangements, tumor prescription dose

Treatment to skeletal lesions and paraspinal lesions may be accomplished with any 3D conformal radiotherapy or intensity-modulated radiotherapy (IMRT) technique suitable for this application with performance specifications adequate to provide proper tumor dose distribution and normal tissue sparing.

At the time of simulation for patients who will receive SABR to the lung and/or liver, the movement of the dome of the diaphragm (superior portion of the liver) is to be observed under fluoroscopy or other acceptable means to estimate respiratory movement during treatment if no

breathing control device is used. Patients will be assessed for suitability for tolerance of a respiratory control device using a breath-hold technique, respiratory gating, or abdominal compression to limit diaphragmatic excursion during respiration. Patients with severe lung disease and patients who cannot tolerate diaphragmatic or breathing control devices for other reasons will be treated without them. A larger margin to account for breathing related intra-fractional organ movement is required.

With the patient is immobilized in a vacuum-type or equivalent body mold, a planning CT scan with 2-5 mm slices is performed. Intravenous contrast is recommended for lesions near mediastinal structures and lesions within the liver. The form of respiratory control to be used during treatment should also be used during the simulation. Oral GI contrast to highlight the stomach and duodenum is recommended for patients with medial liver lesions or lesions of the caudate lobe.

The planning target volume (PTV) is constructed to account for the positional uncertainty of the GTV during treatment. The PTV for each contoured GTV should be at least 5mm larger than the GTV in the axial plane and 1.0 cm larger than the GTV in the cranio-caudal plane. Larger margins may be used in cases where greater motion of the hemi-diaphragm is observed in simulation despite standard maneuvers to diminish motion. For lung SABR the same principles apply; the entire lung volumes are contoured, as are each individual GTV within the lung.

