7.1.2 Special Warnings and Precautions for Use: N/A

7.1.3 Interaction with other medications: None

7.1.4 Adverse Reactions: Sites-specific. Please see section 4.1

7.2 Nivolumab

7.2.1 Contraindications

None

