In CA209003 (n = 296), as of the database lock date of 24-Feb-2012, BMS-936558-related AEs of any grade occurred in 70% of subjects. The most frequent drug-related AEs occurring in $\geq 5\%$ of subjects included fatigue (24%), rash (12%), diarrhea (11%), pruritus (10%), nausea (8%), decreased appetite (8%), hemoglobin decreased (6%) and pyrexia (5%). The majority of events were low grade, with Grade 3/4 drug-related AEs observed in 14% of subjects. The most common Grade 3/4 drug-related AEs occurring in $\geq 1\%$ of subjects were fatigue (2%), pneumonitis (1%), hypoxia (1%), diarrhea (1%), colitis (1%), abdominal pain (1%), AST/ALT increased (1% each), blood alkaline phosphatase increased (1%), lipase increased (1%), pneumonia (1%), hypophosphatemia (1%), and lymphopenia (1%). Drug-related serious AEs (SAEs) occurred in 11% of subjects. Grade 3/4 drug-related SAEs occurring in $\geq 1\%$ of subjects were: pneumonitis (1%), pneumonia (1%), lipase increased (1%), and diarrhea (1%). The spectrum, frequency, and severity of BMS-936558-related AEs were generally similar across dose levels and histological subtypes. Other drug-related AEs included vitiligo, hepatitis, hypophysitis, and thyroiditis. Hepatic or gastrointestinal events were managed with treatment interruption and administration of corticosteroids, and were generally completely reversible. Endocrine events were managed with replacement therapy. Several subjects in these categories successfully reinitiated treatment with BMS-936558. Drug-related pneumonitis occurred in 3% of subjects; Grade ≥ 3 pneumonitis developed in 3 subjects (1%). No clear relationship between the occurrence of pneumonitis and tumor type, dose level, or the number of doses received was noted. Early-grade pneumonitis was generally reversible with treatment discontinuation and corticosteroid administration. In three subjects, infliximab and/or mycophenolate were utilized for additional immunosuppression, with unclear effectiveness. There were three (1%) drug-related deaths due to pneumonitis. In two of these cases, the subject did not receive the early and aggressive intervention (including systemic corticosteroid therapy) that is likely key in the management of this toxicity, while in the third case, other anti-cancer agents (erlotinib and vinorelbine) may have contributed to the fatal event. Preliminary new non-clinical safety findings of adverse pregnancy outcomes and infant losses in the absence of overt maternal toxicity have been reported. The findings of increased late stage pregnancy loss and early infant deaths/euthanasia in Nivolumab exposed pregnant monkeys suggest a potential risk to human pregnancy if there is continued treatment with Nivolumab during pregnancy.

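### The late adverse-event record review covers only GU/GI events, which does not match where SABR is given or the all-CTCAE toxicity objective; under-ascertainment elsewhere is plausible but of unknown size.

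*Combined protocol and SAP*

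**What the plan says.** Section 7.3.1 of the protocol (Late Adverse Events) sets two routes of capture after acute monitoring ends.

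- **Direct reporting, no organ limit.** "These events will include all adverse events reported directly to a member of the study team".
- **Record review, as a supplement.** "In addition, the study team will review encounters in a select specialty category relevant to study endpoints". The records are hospitalization, medical oncology and radiation oncology records, and the review "will be limited in scope based on categorization of events", which the text gives as GU/GI.

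On the treatment, section 4.1.3.1 plans for several kinds of target: "At the time of simulation for patients who will receive SABR to the lung and/or liver" introduces the motion-management rules, and "Treatment to skeletal lesions and paraspinal lesions may be accomplished with any 3D conformal radiotherapy" covers bone and spine. Section 7.1.4 reads: "7.1.4 Adverse Reactions: Sites-specific. Please see section 4.1". For nivolumab, section 7.2.4 states: "There were three (1%) drug-related deaths due to pneumonitis". It also lists endocrine events such as hypophysitis and thyroiditis.

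Toxicity is a secondary objective (2.2.7) and an endpoint (2.4.5). Both are graded by CTCAE, and neither names an organ group.

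**The concern.** The record review is the one late route that can find an event nobody has told the team about. Its filter selects an organ group that matches neither the radiation targets nor the main drug toxicities. Section 4.1.2 steers SABR away from the gastrointestinal tract: patients with esophageal, gastric, intestinal or mesenteric disease are eligible only when no other lesion can be safely targeted. Lung is a SABR target, and pneumonitis is both an endpoint in the lung dose constraints and a nivolumab toxicity. It lies outside the filter.

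Two things are at stake. Late events outside GU/GI could be missed. And because one organ group is searched for while the rest are captured passively, the late-toxicity profile by organ could look more GU/GI than it is. Section 1.4.2 says data on side effects of the combination are sparse, and the group's own experience has 1 to 3 months of follow-up. Late data are therefore among the more useful things the trial can add.

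**Working it through.** The plan states no figure for late ascertainment, so there is none to reproduce. The check sets the sections side by side.

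**1. Filter against endpoints.** Section 7.3.1 explains the selection by relevance to the study endpoints. Objective 2.2.7 and endpoint 2.4.5 are all-CTCAE, and the stopping rule in 7.8 counts Grade 3-5 toxicity without naming an organ. No endpoint is limited to GU/GI. GI is not defined, so it is unclear whether hepatic events are included.

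**2. What each late route can reach.**

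| Route | Organs | What triggers it |
|---|---|---|
| Direct reporting (7.3.1) | All | Someone tells the team |
| AE assessment at follow-up (5.3, 5.4) | All | Scheduled contact |
| Follow-up CT chest, abdomen, pelvis (5.3, 5.4) | Organs imaged | Scheduled scan |
| SAEs to the DSMC (7.5) | All | Team awareness |
| SAEs to the principal investigator (7.7.1) | All | Learning of an SAE during the study or within 30 days of last dose |
| Events more than 30 days after last dose (7.6) | All | Attribution to the agents |
| Record review (7.3.1) | GU/GI only | Active search |

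**3. How often contact is scheduled (5.3).**
- On nivolumab, every 8-12 weeks for two years: 104/12 = 8.7 to 104/8 = 13 visits. In year three, every 4-6 months: 12/6 = 2 to 12/4 = 3. Total over three years: about 10 to 16.
- After nivolumab stops: one visit around 3 months (+/- 2 months) from last dose, then yearly visits or calls. Over three years: about 1 + 3 = 4.
- Section 4.4 adds that patients with progression are followed for survival and are not strictly held to the calendar. Historical median PFS is given as 4-4.6 months (1.4.2), so some may leave the calendar early, although treatment beyond progression is allowed (4.2.1.1).
- For a responder who stops nivolumab, 4.4 and 5.4 suggest the denser schedule and 5.3 the sparser one.

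**4. Size.** Let *r* be the share of late events reaching the team by the organ-neutral routes, and *c* the share of the remainder that record review finds. The recorded share is r + (1 - r)c for GU/GI and r for other organs, so the gap is (1 - r)c. The documents give neither value. Assuming the same *r* in both groups and *c* = 1 (the upper limit):

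| Assumed r | GU/GI recorded | Other recorded | Gap |
|---|---|---|---|
| 1.00 | 100% | 100% | 0 |
| 0.75 | 100% | 75% | 25 points |
| 0.50 | 100% | 50% | 50 points |
| 0.25 | 100% | 25% | 75 points |

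These are assumed values that show the range. The documents favour none of them.

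**5. The late window.** It runs to 3 years post treatment, with progression and death also named, whichever comes first. If progression closes the window, later events fall outside the late definition and the review, whatever the filter. If post treatment means after nivolumab, most of the window is covered by the sparse schedule; if it means after SABR, much of it may be covered by the dense one.

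**The case against.** The strongest reply is that the record review is only a supplement. Direct reporting has no organ limit, AE assessment is scheduled at every follow-up visit and at the yearly contacts after nivolumab, and any inpatient hospitalization counts as an SAE (7.3.1) and goes to the DSMC. Chest imaging is repeated, and section 7.3.1 counts an imaging finding as an adverse event. Suspected fracture and cord compression have their own imaging pathways (6.1.4.5, 6.1.4.6). A GI search is not irrelevant either, since 7.2.4 lists colitis and diarrhea. All of this stands.

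It rules out three stronger readings. A reader might infer that late non-GU/GI events are captured only when volunteered, that pneumonitis would not be looked for, or that the late toxicity rate will be understated. The scheduled assessments and scans contradict the first two; nothing in the documents establishes the third.

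A reader might also size the gap from the pneumonitis rates in 7.2.4 (3% overall, 1% fatal). Those are rates on nivolumab with no timing, so they do not show how many cases fall in the late period. Counting non-GU/GI rows in the dose-constraint tables does not help: it counts tissues in a planning table, including intracranial ones although study SABR is extra-CNS (3.1.5), not events missed.

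The reply does not remove the mismatch. The SAE routes depend on awareness or attribution, and scheduled contact is thinnest after nivolumab stops. Community administration (4.2.1) leaves the study oncologist responsible for reporting, but events may first be seen elsewhere.

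**Conclusion.** The point holds as a mismatch in design. The only active record search for late harm is limited to an organ group that fits neither the treatment nor the toxicity objective, and no reason is given. Under-ascertainment outside GU/GI, and a tilt in the organ profile, are plausible risks of unknown size. They are greatest after nivolumab stops or disease progresses, and for patients treated in the community. The remaining gap is likely to be mainly non-serious events, since serious ones have more routes to the team. The part that concerns progression assumes that the late window stays open afterwards.

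The primary response endpoint is unaffected. Some text in section 7, before the adverse-event monitoring heading and within the SAE reporting section, was not available to this review and could add context, but the restriction in 7.3.1 is explicit.

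**What to change.** Delete the GU/GI limit in section 7.3.1. Alternatively, replace it with all grade 3 or higher events, any event in an organ that received or lay near SABR in that patient, and any immune-related event (including pneumonitis), over the same record types and the same period. If the sponsor prefers to keep the limit, the protocol should say why GU/GI is enough and whether GI includes hepatic events. In either case it should state whether progression closes the late window and whether community records are in scope, because widening the filter cannot reach events outside the window or the records reviewed.

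The cost is modest extra chart-review time in records already being opened for 21 patients. The change concerns data collection only.
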